12.5.2.1.9 Model Assumption Assessment

Potential Period and Sequence effects

To assess potential period and sequence effects, using the primary efficacy model the following outputs will be presented:

- The combined estimates, 95% confidence intervals, and corresponding p-values for each treatment period and each treatment sequence, as well as the difference between treatment periods and between treatment sequences (representing the period term and sequence term combined estimates).
- A plot of the LLMT-6 mean change from baseline at D21 of each treatment arm by treatment period.

In addition, summaries of the pre-dose baseline values for each treatment period (e.g., period baseline values) and overall per treatment arm will be explored from the descriptive statistics table presented in [Section 12.5.2.3.3](#).

Distribution of Residual and Outliers search

The distribution of residuals as well as the search for potential outliers will be based on the analysis of primary endpoint using a LME model for cross-over data (as described in [Section 12.5.2.1.8](#)) but using observed cases LLMT-6 scores (not following any missing data MI strategy).

Distribution of the residuals will be assessed, based on outcome of the primary efficacy endpoint as follows:

- The normality of the residuals will be graphically assessed presenting boxplot, histogram, QQ-plots and scatterplot of residual versus linear predictors, based on studentized residuals obtained from the primary efficacy model.
- The distribution of the residuals obtained from the primary efficacy model will also be assessed using boxplots with each category of the fixed effect (treatment arm, treatment sequence and treatment period)

If the residuals appear not to be normally distributed, alternative approaches such as transformation of the data and nonparametric analyses may be considered to express treatment effect.

Outliers search: Outliers will be identified based on diagnosis performed from primary outcome measure using boxplot, and scatterplot of residual versus linear predictors,

If outliers are present, additional sensitivity analyses may be conducted with outliers excluded to assess their impact on the results.

12.5.2.2 Sensitivity Analysis – Tipping Point

The primary efficacy analysis assumes data are either missing at random or missing not at random as per missing data handling strategy described in [Section 12.5.2.1.6](#)

To assess the robustness of the treatment effect with regard to missing data, a sensitivity analysis based on a tipping point analysis will be performed for the primary efficacy endpoint to assess the impact of missing data assumed MNAR on the primary estimand.

This analysis will impute missing nabiximols D21 data under a Missing Not at Random assumption, using the FAS, during the 51-day randomized efficacy period (see [Section 10.1](#)).

Thus, when no penalty is added the tipping point analysis is the equivalent to the primary efficacy analysis.

Tipping point analyses

Using monotone datasets generated as described in [Section 12.5.2.1.5](#), the remaining missing data will be imputed separately for each treatment period and each treatment arm using the REGRESSION method in conjunction with the MONOTONE statement and either MNAR statements (for nabiximols treatment arm following imputation strategy described in [Table 12.5-1](#)) or MAR statement (for either placebo treatment arm or nabiximols treatment arm following imputation strategy described in [Table 12.5-1](#)) of the SAS® MI procedure.

- Step1, the imputation model will create 300 monotone datasets, as described in [Section 12.5.2.1.5](#)
- Step 2
 - Step2a for Period 1 - first model

Imputed missing D21 LLMT-6 scores for patients on placebo treatment arm with non-missing baseline score and missing D21 LLMT-6 score as well as for patients on nabiximols treatment arm with non-missing baseline LLMT-6 score and missing D21 LLMT-6 scores due to COVID-19 will remain MAR (no delta addition) and MI will follow the same approach as the one described in [Section 12.5.2.1.6](#) Step 2a

The first imputation model (e.g., delta=0) to impute missing D21 LLMT-6 scores for patients on nabiximols treatment arm with non-missing baseline scores and missing LLMT-6 scores not due to COVID-19 will follow the same MNAR placebo-based MI approach as the one described in [Section 12.5.2.1.6](#) Step 2a.

- Step2b for Period 2 - first model

Imputed missing D21 LLMT-6 scores for patients on placebo treatment arm with missing D21 LLMT-6 score as well as for patients on nabiximols treatment arm with either missing D21 LLMT-6 scores due to COVID-19 for those entered in Period 2 or due to study withdrawal during Period 2 will remain MAR (no delta addition) and MI will follow the same approach as the one described in [Section 12.5.2.1.6](#) Step 2b;

The first imputation model (e.g., delta=0) to impute missing D21 LLMT-6 scores for patients on nabiximols treatment arm entered in Period 2 with missing D21 LLMT-6 scores not due to COVID-19 will follow the same MNAR placebo-based MI approach as the one described in [Section 12.5.2.1.6](#) Step 2b.

- Step2c subsequent models

Separately for each treatment period, missing D21 LLMT-6 scores imputed under MAR at Step 2a or Step 2b will remain MAR (no delta addition) whereas for D21 LLMT-6 scores imputed under MNAR at Step 2a or Step 2b, in subsequent models, a common (non-zero) delta value (where delta value represents LLMT-6 score ranging from 0.12 to 5) will be added following MNAR imputation to each imputed value. Delta addition will be obtained using the DELTA option of the MNAR statement of the SAS® MI procedure.

For the first imputation model (delta=0) 300 imputed datasets will be generated at Step 2a and Step 2b. For the subsequent models (delta >0), the same monotone datasets as those used for first imputation model (delta=0) will be retrieved.

- Step 3, the 300 imputation datasets generated from each delta values will be analyzed by a LME model for crossover data applied to D21 as described in [Section 12.5.2.1.8](#).
- Step 4, for each value of delta, results from each LME model for crossover data as described in [Section 12.5.2.1.8](#) will be combined as described in [Section 12.5.2.1.7](#).
- Step 5, the tipping point will correspond to the first instance where the primary inference changes (i.e., $p \geq 0.05$ for between treatment arm difference in LSmeans). Consequently, the testing (Step 2 to Step 4) will be repeated for a plausible $nabiximols$ value using a grid search method. Firstly, larger changes in delta values (delta will range from 0 to 5 by increments of 5/6 where 5/6 represents the maximum effect of an individual MAS transformed score on LLMT-6) will be used. If the primary inference changes, then smaller changes in delta values (1/6 representing the change of 1 in LLMT-6) will be used to identify a more accurate tipping point between the last two delta values which were using larger changes (ie. last delta value with $p < 0.05$ and first delta value with $p \geq 0.05$).
- Step 6, results corresponding to each delta values will be presented within a summary table including combined LS mean estimate and corresponding SE and 95% CI for each treatment arm along with the combined LS mean estimate of the difference versus placebo along with its corresponding SE and confidence interval. The tipping point will be identified.

12.5.2.3 Supplementary Analyses Based on LLMT-6

12.5.2.3.1 Subgroup Analysis for Primary Endpoint

The treatment effect across the different subgroups indicated in Table 12.5-2 will be explored on the primary efficacy endpoint: LLMT-6.

Table 12.5-2 Subgroup Analyses of Primary Efficacy Endpoint

Group variables	Subgroup	Comments
Sex	Male Female	
Prior cannabis use	Yes No	
Baseline LLMT-6 category (cut off=2)	Period 1 baseline LLMT-6 <= 2 Period 1 baseline LLMT-6 > 2	Baseline LLMT-6 categories refers to period 1 baseline score
Baseline LLMT-6 category (cut off=3)*	Period 1 baseline LLMT-6 <= 3 Period 1 baseline LLMT-6 > 3	

If the value of a group variable cannot be determined, the patient will be excluded from the corresponding subgroup analysis.

The treatment arm-by-subgroup interaction will be assessed for the primary efficacy endpoint using the 300 imputation datasets derived to perform the primary efficacy analysis as described in [Section 12.5.2.1.6](#). Each imputed dataset will be analysed using linear mixed-effects model for crossover data as described in [Section 12.5.2.1.8](#) with subgroup and subgroup-by-period level treatment arm interaction, as 2 additional fixed effects. Result from each linear mixed-effects model for crossover data will then be combined as described in [Section 12.5.2.1.7](#).

For each subgroup analyses, the following estimates will be presented. Within each subgroup; (i) the combined adjusted LS mean (SEs and 95% CIs) of the change from period baseline to D21 for nabiximols and placebo will be presented, (ii) the combined difference in LS means (nabiximols–placebo) together with SEs and 95% CIs as well as the nominal p-value will be presented. The subgroup-by-treatment arm interaction nominal p-value will be presented. In addition, frequency count and descriptive statistics for each subgroup will be presented in a separate table. Forest plots will be used to present subgroup analyses results. The forest plot created from subgroup analyses will display number of patients, all combined estimates (i, ii), including combined 95% CI for (ii) and interaction p-values.

If, in each treatment arm by subgroup, the number of patients is less than 5, only summary statistics will be displayed and no subgroup analyses will be conducted.

As the study is not stratified by site it is not planned to explore the impact of site on the treatment effect. However, if deemed necessary the impact of MAS assessors on LLMT-6 will be looked at.

12.5.2.3.2 Response Analyses Based on LLMT-6

The reduction from baseline to D21 of respectively $\geq 20\%$, $\geq 30\%$, $\geq 40\%$, $\geq 50\%$ (as described in [Section 10.16](#)) will be analyzed using a logistic regression applied to crossover design using a generalized estimating equation (GEE). The models will be analyzed using the SAS® GLIMMIX procedure with a logit link function and a binary distribution. The marginal log likelihood will be approximated with an adaptive Gauss-Hermite quadrature (obtained using the EMPIRICAL option of the SAS® GLIMMIX procedure) using a likelihood-based sandwich estimator.

The preferred model will include a period level LLMT6 baseline covariate, treatment arm, treatment period, and treatment sequence as fixed effect.

An unstructured covariance will be used to model the residual errors between LLMT-6 scores within the same patient across period. The denominator degrees of freedom will be calculated according to the Kenward-Roger method (e.g. KR2, 2009 version).

This model will provide, for each response analysis, at D21, the estimate of the odds ratios (OR) representing the odds in nabiximols treatment arm versus placebo treatment arm and corresponding 95% CI and nominal p-value. These parameters will be summarized by treatment arm along with number of responders and associated crude response rates.

If less than 5 patients in either treatment arm are considered as responders, only descriptive statistics will be conducted presenting the number and percentage of responders by treatment arm.

In case of non-convergence, appropriate model will be applied.

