12.5.5.1 Timed 25-Foot Walk (T25FW)

A decrease in average time to complete the two trials will show an improvement.

The difference between treatment arms in the change from baseline to D21 in average 25-foot walk time (as defined in [Section 10.17](#)) will be analyzed using the same LME model for crossover data as the one used for the primary analysis of the primary efficacy endpoint (as described in [Section 12.5.2.1.8](#)). As a sensitivity analysis, the same analysis will be repeated using non-imputed average 25-foot walk times (as defined in [Section 10.17](#)).

If model diagnostics suggests that the residuals are not normally distributed a non-parametric analysis will be conducted.

A $\geq 20\%$ reduction from baseline to D21 of in average time (as described in [Section 10.17](#)) will be analyzed using a logistic regression applied to crossover design using a GEE (as described in [Section 12.5.2.3.2](#)).

A histogram presenting LS means change from baseline estimates along with their corresponding 95% CI will be provided by treatment arm.

Descriptive statistics for the average T25FW values change from baseline and percentage change from baseline by treatment arm will be provided; as well as a by-patient listing presenting observed and derived variables.

12.5.5.2 11-point Numerical Rating Scale Score (NRS-spasticity score)

The 11-point NRS spasticity scale is composed of 11 items ranging from 0 (no spasticity) to 10 (maximal spasticity) to assess the overall spasticity in patients with MS during the last 24 hours.

The difference between treatment arms in the 7-day average NRS spasticity score over the last 7 day preceding D21 of each period (as defined in [Section 10.18](#)) will be analyzed using a linear mixed model for crossover data using the SAS® GLIMMIX procedure with an identity link function and a normal distribution. The 7-day average NRS spasticity D21 score will be included as the dependent variable. Hence, each patient will contribute two measurements to the model, one for each period of the study.

The preferred model will include period level treatment arm, treatment period, and treatment sequence as fixed effects. Unstructured (UN) covariance structure will be used to model the repeated 7-day average NRS spasticity scores. The denominator degrees of freedom will be calculated according to Kenward-Roger method (e.g., KR2, 2009 version).

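### The responder analysis combines GEE, quadrature and Kenward-Roger elements that cannot be fitted together, and does not say which kind of odds ratio it reports (minor)

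*SAP*

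**What the plan says.** SAP 12.5.2.3.2 covers reductions in LLMT-6 of at least 20%, 30%, 40% and 50% from baseline to D21. For this one analysis it specifies:

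- **Framework.** The outcome "will be analyzed using a logistic regression applied to crossover design using a generalized estimating equation (GEE").
- **Software, link, distribution.** "The models will be analyzed using the SAS® GLIMMIX procedure with a logit link function and a binary distribution".
- **Likelihood.** "The marginal log likelihood will be approximated with an adaptive Gauss-Hermite quadrature".
- **Variance.** Described as "obtained using the EMPIRICAL option of the SAS® GLIMMIX procedure) using a likelihood-based sandwich estimator".
- **Model terms.** "The preferred model will include a period level LLMT6 baseline covariate, treatment arm, treatment period, and treatment sequence as fixed effect". No random effect is listed.
- **Within-patient dependence.** "An unstructured covariance will be used to model the residual errors between LLMT-6 scores within the same patient across period".
- **Degrees of freedom.** Kenward-Roger, KR2 version.
- **Output.** An odds ratio for nabiximols against placebo with a 95% CI and nominal p-value, beside responder counts and crude rates.
- **Fallback.** "In case of non-convergence, appropriate model will be applied".

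SAP 12.5.5.1 applies the same method to a 20% reduction in T25FW time, which "will be analyzed using a logistic regression applied to crossover design using a GEE", by reference back to 12.5.2.3.2. SAP Appendix 14 (entries P1 SUP2 and E2 SUP1) says only that the odds ratio comes from a logistic regression for crossover data adjusted for period baseline.

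**The concern.** These elements come from different estimation approaches. GEE solves estimating equations for a marginal mean model and maximises no likelihood. Quadrature evaluates a likelihood after integrating out a random effect. Kenward-Roger corrects the model-based covariance of a linear or linearised mixed model. A programmer cannot satisfy all of them at once, so some instruction has to be dropped and the SAP does not say which.

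The choice between GEE and quadrature also fixes the estimand. A marginal model gives a population-averaged odds ratio and a random-effects model gives a patient-specific one. Five comparisons inherit the text (four LLMT-6 thresholds and one for T25FW), and a reader of the report could not tell which kind of odds ratio is shown.

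The fallback does not help. It names no model, and it is triggered by non-convergence, not by an incoherent specification. SAP 6.1 places the efficacy analyses after database lock and unblinding, so by inference (the section does not say so) any substitute would be chosen with treatment known. By contrast, SAP 12.5.2.1.8, 12.5.4.2 and 12.5.5.2 each name compound symmetry as their fallback.

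**Working it through.** The plan states no figure for this analysis, so there is nothing to reproduce. The check sets the instructions side by side and then sizes the ambiguity.

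**Step 1: which instructions fit together**

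| Instruction in SAP 12.5.2.3.2 | Marginal model (GEE) | Random-effects logistic model |
|---|---|---|
| GEE label | yes | no |
| Fixed effects only | yes | no, a random effect is needed |
| Residual or working covariance across periods | yes | no, dependence comes from the random effect |
| Log likelihood by adaptive quadrature | no, there is no likelihood | yes |
| Likelihood-based sandwich | no, a GEE sandwich is built from the estimating equations | yes |
| Kenward-Roger degrees of freedom | no, not with a sandwich variance | no, not with a quadrature likelihood |

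Neither column satisfies every row. With no random effect in the model, quadrature has nothing to integrate over. This rests on what the methods are; how the SAS procedure would respond to such code was not tested.

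The covariance sentence refers to LLMT-6 scores, although the response is binary. SAP 12.5.4.2 has a nearly identical sentence, with the same Kenward-Roger clause, for the continuous repeated-measures model. The text may have been carried over from there.

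**Step 2: how far the two odds ratios differ**

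Inputs, all assumed because the documents give neither a responder rate nor a between-patient SD: placebo response 20% or 30%; patient random-intercept SD σ from 0.5 to 3; patient-specific odds ratio 2.0 or 3.0.

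With z standard normal and T = 1 for nabiximols and 0 for placebo:

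- p_T = E_z[ expit(b0 + T·ln(OR_patient) + σz) ], with b0 set so that p_0 equals the placebo rate.
- OR_population = [p_1/(1 − p_1)] / [p_0/(1 − p_0)].

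Example: p_0 = 0.20, OR_patient = 3.0, σ = 1. Gauss-Hermite integration gives p_1 = 0.388, so OR_population = (0.388/0.612)/(0.20/0.80), about 2.53.

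| σ | Patient-specific 2.0: population-averaged at 20% / 30% | Patient-specific 3.0: population-averaged at 20% / 30% |
|---|---|---|
| 0.5 | 1.94 / 1.93 | 2.85 / 2.83 |
| 1 | 1.81 / 1.78 | 2.53 / 2.49 |
| 1.5 | 1.67 / 1.64 | 2.24 / 2.19 |
| 2 | 1.56 / 1.53 | 2.01 / 1.96 |
| 3 | 1.41 / 1.39 | 1.71 / 1.67 |

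For a patient-specific odds ratio of 3.0, the gap runs from (3.0 − 2.85)/3.0 = 5% to (3.0 − 1.67)/3.0 = 44%. The two coincide at σ = 0.

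**Step 3: the same data fitted both ways**

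A two-period crossover was simulated with 68 patients (the re-estimated number of completers in SAP 8.2), a true patient-specific odds ratio of 2.5 and 200 replicates. Treatment, period and sequence were fitted, without a baseline covariate. The random-intercept model used non-adaptive quadrature. Median odds ratios were:

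- σ = 1: GEE 2.24, random-intercept model 2.60.
- σ = 2: GEE 1.89, random-intercept model 2.76 (199 usable replicates).

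**The case against.** The strongest reply is that the plan leans clearly one way. It names GEE first, 12.5.5.1 repeats the label, the terms are fixed effects only and the dependence is placed on residuals. All of that describes a population-averaged model with a stray quadrature clause. To obtain a patient-specific odds ratio, a programmer would have to add a term the SAP does not contain. This stands: a reader might infer that the two odds ratios are equally supported, and the text does not bear that out. What remains is that the quadrature, likelihood-based sandwich and Kenward-Roger instructions cannot be followed under that reading, and that no section labels the odds ratio.

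Other parts of the defence also hold:

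- A reader might take the unstructured residual covariance as a further conflict with GEE. It is not one. With two periods there is a single within-patient correlation, so unstructured and exchangeable working correlations are the same.
- Kenward-Roger affects standard errors and degrees of freedom, not which odds ratio is estimated.
- The size of the gap depends on assumed inputs and is small at σ = 0.5. Both odds ratios equal 1 under no effect and lie on the same side of 1, so no change of conclusion has been shown.
- Crude response rates are reported beside the odds ratio, and the output is descriptive only if fewer than 5 patients respond in either arm.

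**Conclusion.** The specification in SAP 12.5.2.3.2, and its re-use in 12.5.5.1, is incoherent and has to be rewritten before it can be programmed. This is more than a missing detail, because instructions that are present exclude each other. If the population-averaged and patient-specific readings were confused, the difference could range from slight to substantial, as the Step 2 table shows under its assumed response rates and SDs.

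Severity is minor. Appendix 14 classes both analyses as supplementary, the T25FW one to an exploratory endpoint. They carry nominal p-values and lie outside the LLMT-6 then LLMT-4 testing hierarchy. A reader might infer that the efficacy conclusion is in doubt. The documents do not support that, since the primary and secondary analyses use a separately specified linear mixed model.

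**What to change.** Revise SAP 12.5.2.3.2 before unblinding, keeping the first-named method:

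1. Specify a GEE with logit link, one within-patient working correlation over the two periods (unstructured or exchangeable), the fixed effects already listed, and a small-sample-corrected sandwich variance.
2. Delete the quadrature, likelihood-based sandwich and Kenward-Roger text.
3. Describe the correlation as between the binary responses in the two periods, not between LLMT-6 scores.
4. Label the odds ratio population-averaged in 12.5.2.3.2, 12.5.5.1 and both Appendix 14 entries.
5. Replace the open fallback with a named one: GEE with an independence working correlation.

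A random-intercept logistic model fitted by adaptive quadrature would be equally coherent, provided the residual covariance and Kenward-Roger text is removed and the odds ratio is labelled patient-specific. What matters is that one model is chosen before unblinding. The cost is SAP wording and the matching analysis code; no new data are needed.

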12.5.2.3.3 Summary Descriptions and Listings

LLMT-6 values, change from baseline and percentage change from baseline in LLMT-6 will be summarized by treatment arm, per treatment period and overall, over time.

Mean \pm SD LLMT-6 values and change from baseline by visit and treatment arm will be plotted.

Scatterplots of the change from baseline to D21 and percentage change from baseline to D21 in LLMT-6 against the baseline LLMT-6 will also be produced.

Spaghetti plots presenting baseline, D1H3 and D21 LLMT-6 scores from both treatment periods will be plotted for each patient by treatment arm. Paneled by treatment period and the treatment received in that period differentiated by line pattern.

Cumulative distribution functions on change from baseline and relative change from baseline to D21 in LLMT-6 will be plotted by treatment arm.

A by-patient listing will be provided for LLMT-6 observed, change and relative change from baseline along with responder status (as defined in [Section 12.5.2.3.2](#)).

